## **SYNOPSIS**

**TITLE:** A Placebo-Controlled, Double-Blind, Randomized, Phase 2 Study to Evaluate the Effect of Obicetrapib 10 mg Daily in Combination With Ezetimibe 10 mg Daily as an Adjunct to High-Intensity Statin Therapy: The ROSE 2 Study

PROTOCOL NUMBER: TA-8995-202

**INVESTIGATIONAL PRODUCT:** Obicetrapib

PHASE: 2

**INDICATION:** Dyslipidemia

#### **OBJECTIVES:**

The primary objective of this study is to evaluate the effect of objectrapib 10 mg + ezetimibe 10 mg combination therapy compared with placebo, when used as an adjunct to high-intensity statin therapy, on low-density lipoprotein cholesterol (LDL-C) at Day 84.

The secondary objectives of this study include the following, in hierarchical order:

- To evaluate the effect of obicetrapib 10 mg monotherapy compared with placebo, when used as an adjunct to high-intensity statin therapy, on LDL-C at Day 84;
- To evaluate the effect of obicetrapib 10 mg + ezetimibe 10 mg combination therapy compared with placebo, when used as an adjunct to high-intensity statin therapy, on apolipoprotein B (ApoB) at Day 84; and
- To evaluate the effect of obicetrapib 10 mg monotherapy compared with placebo, when used as an adjunct to high-intensity statin therapy, on ApoB at Day 84.

The exploratory objectives of this study include the following:

- To evaluate the effect of obicetrapib 10 mg + ezetimibe 10 mg combination therapy and obicetrapib 10 mg monotherapy, when used as an adjunct to high-intensity statin therapy, on non-high-density lipoprotein cholesterol (non-HDL-C), very low-density lipoprotein cholesterol (VLDL-C), high-density lipoprotein (HDL) cholesterol (HDL-C), triglycerides (TG), apolipoprotein E (ApoE), lipoprotein (a) (Lp[a]), and HDL-ApoE at Day 84;
- To evaluate the effect of obicetrapib 10 mg + ezetimibe 10 mg combination therapy and obicetrapib 10 mg monotherapy, when used as an adjunct to high-intensity statin therapy, on the proportion of participants achieving predefined LDL-C targets at Day 84;

- To assess the mean trough plasma levels of obicetrapib 10 mg + ezetimibe 10 mg combination therapy and obicetrapib 10 mg monotherapy at steady state on Days 28, 84, and 112; and
- To evaluate the safety and tolerability profiles of obicetrapib 10 mg + ezetimibe 10 mg combination therapy and obicetrapib 10 mg monotherapy, when used as an adjunct to high-intensity statin therapy, assessed by clinical laboratory values and incidence of adverse events (AEs).

#### **POPULATION:**

The population for this study includes men and women 18 to 75 years of age, inclusive, with a body mass index <40 kg/m², fasting LDL-C levels >70 mg/dL, and TG levels <400 mg/dL at the Screening Visit, who are currently receiving high-intensity statin therapy.

#### STUDY DESIGN AND DURATION:

This study will be a placebo-controlled, double-blind, randomized, Phase 2 study to evaluate the efficacy, safety, and tolerability of obicetrapib 10 mg, both in combination with ezetimibe 10 mg and as monotherapy, as an adjunct to high-intensity statin therapy. This study will take place at approximately 20 sites in the United States.

# Screening Period

At the Screening Visit, participants will be required to sign an informed consent form (ICF) before any study-related procedures are performed. After signing the ICF, participants will be assessed for study eligibility.

## **Treatment Period**

Up to 2 weeks after the Screening Visit, participants will return to the site on Day 1 (Visit 2) and confirm study eligibility before being randomized and beginning treatment. Approximately 114 eligible participants (38 participants per treatment group) will be randomized in a 1:1:1 ratio to 1 of the following treatment groups:

- Combination therapy: Obicetrapib 10 mg + ezetimibe 10 mg (administered as one 10 mg obicetrapib tablet and one 10 mg ezetimibe capsule);
- Obicetrapib monotherapy: Obicetrapib 10 mg (administered as one 10 mg obicetrapib tablet and 1 placebo capsule); or
- Placebo (administered as 1 placebo tablet and 1 placebo capsule).

During the 12-week Treatment Period, the assigned study drugs will be administered by the participants orally with water, once daily on Day 1 to Day 84 at approximately the same time each morning. Participants will return to the site on Day 28 (±2 days), Day 84 (±2 days), and Day 112 (±2 days) for efficacy, safety, and pharmacokinetic (PK) assessments. Participants, Investigators, the Clinical Research Organization, and the Sponsor will be blinded to all lipid results from Day 1 (Visit 2) for the first participant until all enrolled participants complete the Day 84 (End of Treatment) visit or are withdrawn from the study, in order to protect blinding to treatment assignment.

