#### 4 SELECTION AND WITHDRAWAL OF PARTICIPANTS

## 4.1 Inclusion Criteria

Participants who meet all of the following criteria will be eligible to participate in the study:

- 1. Understanding of the study procedures, willingness to adhere to the study schedules, and agreement to participate in the study by giving written informed consent prior to screening procedures;
- 2. Men or women 18 to 75 years of age, inclusive, at the Screening Visit;
  - Women may be enrolled if all 3 of the following criteria are met:
    - They are not pregnant;
    - They are not breastfeeding; and
    - They do not plan on becoming pregnant during the study.
  - Women of childbearing potential must have a negative urine pregnancy test at the Screening Visit. Note: Women are not considered to be of childbearing potential if they meet 1 of the following criteria as documented by the Investigator:
    - They have had a hysterectomy or tubal ligation at a minimum of 1 cycle prior to signing the ICF; or
    - They are postmenopausal, defined as ≥1 year since their last menstrual period for women ≥55 years of age or ≥1 year since their last menstrual period and have a follicle-stimulating hormone (FSH) level in the postmenopausal range for women <55 years of age.

  - O Women of childbearing potential must agree to use an effective method of avoiding pregnancy from screening to 90 days after the last visit. Men whose partners are of childbearing potential must agree to use an effective method of avoiding pregnancy from screening to 90 days after the last visit. Effective methods of avoiding pregnancy are contraceptive methods with a Pearl index of <1 used consistently and correctly (including implantable contraceptives, injectable contraceptives, oral contraceptives, transdermal contraceptives, intrauterine devices, diaphragm with spermicide, male or female condoms with spermicide, or cervical cap) or a sterile sexual partner.
- 3. Fasting LDL-C levels >70 mg/dL and TG levels <400 mg/dL at the Screening Visit; and
- 4. Currently receiving high-intensity statin therapy (atorvastatin 40 or 80 mg or rosuvastatin 20 or 40 mg) at a stable dose for 8 weeks prior to screening and intending to remain at the same stable dose throughout the study duration.

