## 8.4 Pregnancy Reporting

If a participant becomes pregnant during the study or within the Safety Follow-up Period defined in the protocol, the Investigator is to stop dosing with study drug(s) immediately and the participant should be withdrawn from the study. Early termination procedures should be implemented at that time.

A pregna	ancy	is not considered	to b	e an AE or	SA	E; how	ever, it	must b	e rep	ported to	
		within 24 hour	s of	knowledge	of t	he ever	nt.			wil	1 then
provide	the	Investigator/site	the	Exposure	In	Utero	(EIU)	form	for	completion.	The
Investiga	ator/s	ite must complete	the l	EIU form aı	nd fa	x/email	l it back	to			

If the female partner of a male participant becomes pregnant while the participant is receiving study drug or within the Safety Follow-up Period defined in the protocol, the Investigator should notify as described above.

The pregnancy should be followed until the outcome of the pregnancy, whenever possible. Once the outcome of the pregnancy is known, the EIU form should be completed and faxed/emailed to

. If the outcome of the pregnancy meets the criteria for immediate classification as an SAE (ie, postpartum complication, spontaneous abortion, stillbirth, neonatal death, or congenital anomaly), the Investigator should follow the procedures for reporting an SAE.

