## 8.7.2 Endocrinology Assessments

A urine pregnancy test will be performed for women of childbearing potential at the Screening Visit prior to their participation in the study and at the Early Termination Visit (if indicated).

An FSH test will be performed at the Screening Visit prior to participation in the study in women <55 years of age for whom it has been ≥1 year since their last menstrual period.

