# **APPENDIX A: SCHEDULE OF PROCEDURES**

	Screening a,b	Treatment Period			Safety Follow-Up		
Visit	1	2 (Baseline)	3	4 (EOT)	5		
Week	Up to -2	0	4	12	16	Early Termination Visit	
Day (±Visit Window)	-14 to -1	1	28 (±2)	84 (±2)	112 (±2)	Unscheduled	
Informed consent c	X						
Inclusion/exclusion criteria	X	$X^d$					
Demographic information	X						
Medical/surgical history	X						
Prior/concomitant medications	X	X	X	X	X	X	
Weight and height e	X						
Physical examination	X			X			
Vital signs f	X	X	X	X	X	X	
12-lead ECG g	X						
Urine pregnancy test h	X					X	
FSH test i	X						
Fasting (approximately 10 hours)							
chemistry and hematology j	X	X	X	X	X	X	
Fasting (approximately 10 hours)							
lipid profile k	X	X	X	X		X	
PK sample 		X	X	X	X m	X	
Fasting (approximately 10 hours)							
aldosterone		X	X	X	X	X	
Fasting (approximately 10 hours)							
Lp(a)		X		X			
Serum archive sample n		X		X			
Randomization		X					
Dispense study drug o		X	X				
Study drug administration p			X				
Study drug compliance			X	X			
Register visit in IRT	X	X	X	X		X	
Adverse events		X	X	X	X	X	

Note: When several assessments are required at the same visit, samples for clinical laboratory assessments should be collected after completing other assessments, such as physical examinations, vital signs, and 12-lead ECGs.

Note: In cases of COVID-19 limitations, it is the Investigator's responsibility to assure the safety of participants. If necessary, the Sponsor will implement and document mitigation strategies as described in Section 3.1.4. In the absence of a COVID-19 impact, it is expected that Investigators and participants follow the protocol requirements as set forth.

Note: For the purposes of this study, fasting will be defined as nothing by mouth except water and any essential medications.

- a. If laboratory abnormalities during screening are considered by the Investigator to be transient, then the laboratory tests may be repeated once during screening. The Investigator's rationale for retesting should be documented. If the retest result is no longer exclusionary, the participant may be randomized.

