- b. A participant who is screened and does not meet the study eligibility criteria may be considered for rescreening upon Sponsor and/or Medical Monitor consultation and approval. Rescreened participants will be assigned a new participant number. Rescreening should occur no less than 5 days after the last Screening Visit.
- c. Participants will be required to sign an ICF before any study-related procedures are performed.
- d. Confirm the participant continues to meet the inclusion and exclusion criteria and assess any updates since the Screening Visit.
- e. Weight and height will be measured at the Screening Visit and will be used to calculate body mass index. Measurement of weight should be performed with the participant dressed in indoor clothing, with shoes removed, and bladder empty.
- f. Vital signs will include body temperature, heart rate, and triplicate blood pressure (systolic and diastolic) measurements. Participants should be in the supine position after at least 10 minutes rest prior to the vital sign measurements.
- g. A single, standard 12-lead ECG will be performed by the Investigator or trained site personnel at the Screening Visit and read locally.
- h. For women of childbearing potential only.
- i. FSH test will be performed in women <55 years of age for whom it has been ≥1 year since their last menstrual period.
- j. At the Screening Visit only, chemistry panel will include HbA1c.
- k. LDL-C level will be calculated using the Friedewald equation unless TG≥400 mg/dL or LDL-C ≤50 mg/dL; in both cases, LDL-C level will be measured directly by preparative ultracentrifugation, also referred to as beta quantification (Source: LDL calculated. MDCalc. https://www.mdcalc.com/ldl-calculated. Accessed 10 August 2021). Additionally, LDL-C will be measured by preparative ultracentrifugation, also referred to as beta quantification, at baseline (Visit 2) and at the end of the 12-week Treatment Period (Visit 4) for all participants.
- 1. At visits with dosing scheduled (ie, Visits 2, 3, and 4), PK samples will be collected with fasting laboratory samples (pre-dose). At Visits 3 and 4, the time between the last dose of study drug and PK sampling will be >24 hours. The subsequent post-dose PK sample at Visit 5 should be collected at approximately the same time as the previous visits.

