3 STATISTICAL METHODOLOGY

3.1 General Considerations

3.1.1 Analysis Day

Analysis day will be calculated from the date of first dose of study drug. The day of the first dose of study drug will be Day 1, and the day immediately before Day 1 will be Day -1. There will be no Day 0.

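### No pregnancy test is scheduled on Day 1 or during dosing; the only routine test is at Screening, up to 14 days before the first dose

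*Protocol*

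**What the plan says.** Protocol Section 4.1, inclusion criterion 2, admits women only if they are not pregnant, not breastfeeding and not planning a pregnancy during the study. It adds a testing requirement, "Women of childbearing potential must have a negative urine pregnancy test at the Screening Visit", and a contraception requirement, "Women of childbearing potential must agree to use an effective method of avoiding pregnancy from screening to 90 days after the last visit".

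Section 8.7.2 places the urine test "at the Screening Visit prior to their participation in the study and at the Early Termination Visit (if indicated"). The row "Urine pregnancy test" in Appendix A agrees: it is marked under Screening and Early Termination and is blank for Visits 2 to 5. Appendix B lists the test without adding a visit.

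For Day 1, the Synopsis (Treatment Period) and Section 3.1.2 say that "participants will return to the site on Day 1 (Visit 2) and confirm study eligibility before being randomized and beginning treatment". Appendix A, footnote d, gives the site's task at that visit: "Confirm the participant continues to meet the inclusion and exclusion criteria and assess any updates since the Screening Visit". If a pregnancy occurs during the study, Section 8.4 says "the Investigator is to stop dosing with study drug(s) immediately and the participant should be withdrawn from the study".

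**The concern.** Visit 2 is the last point at which exposure of a pregnancy to study drug can be avoided altogether. The protocol asks the site to reconfirm eligibility there but attaches no objective check to the one criterion that can change unnoticed between Screening and Day 1. The written test requirement is tied to the Screening Visit, so the Day 1 confirmation can be completed without a new test.

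During treatment, the stop-dosing rule in Section 8.4 and the pregnancy withdrawal reason in Section 4.5 take effect only once someone knows of the pregnancy. With no scheduled test on treatment, that depends on the participant's report or on clinical suspicion. At Visit 3 she receives two more kits and is next due on Day 84.

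What is at stake is participant safety, not the efficacy analysis.

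**Working it through.** The plan gives no figure of its own on this point. The check is a reading of the schedule plus day counts.

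**Inputs**

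- Screening falls on Day -14 to Day -1 (Appendix A).
- First dose is on Day 1. There is no Day 0; SAP Section 3.1.1 states that "the day immediately before Day 1 will be Day -1".
- Visit 3 is on Day 28 ± 2 and Visit 4 on Day 84 ± 2 (Appendix A).
- Scheduled urine tests: Screening; Early Termination if indicated (Section 8.7.2, Appendix A).

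**Screening test to first dose**

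- Longest: Day -14 to Day -1 is 13 days, and Day -1 to Day 1 is 1 day, so 13 + 1 = 14 days.
- Shortest: Day -1 to Day 1 = 1 day.

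**Longest interval without a scheduled test, from Screening to Visit 4, for a woman who completes treatment**

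| Schedule | Calculation | Days | With visit windows |
|---|---|---|---|
| As written | 14 + (84 − 1) | 97 | 14 + (86 − 1) = 99 |
| Day 1 test added | 84 − 1 | 83 | 86 − 1 = 85 |
| Day 1 and Visit 3 tests added | larger of 28 − 1 = 27 and 84 − 28 = 56 | 56 | 86 − 26 = 60 |

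Under the plan as written, a completer has no scheduled pregnancy test at any visit after Screening.

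**Do the other provisions close the gap before dosing?**

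- *Contraception* is required from Screening onward. It cannot act on a conception shortly before Screening, which may be too early for the urine test that day but detectable by Day 1. It prevents pregnancy; it does not detect one.
- *The Early Termination test* is conditional and applies only to participants who are already stopping.
- *Day 1 confirmation* covers the criterion, but no procedure is attached to it.

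None of the three supplies a test before the first dose.

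**The case against.** The strongest reply is that the protocol is consistent and already layered. It combines a negative test no more than 14 days before dosing, exclusion of women planning pregnancy, contraception with a Pearl index below 1, reconfirmation on Day 1, and rules to stop dosing, report within 24 hours and follow the pregnancy to outcome. Nothing prevents an investigator from testing on suspicion.

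The expected count is also small. A Pearl index below 1 means fewer than 1 pregnancy per 100 woman-years. If all 114 participants were women of childbearing potential, the 14-day gap would give fewer than 114 × 14/365 × 0.01 = 0.044 pregnancies in the whole trial. If one third were (an assumption, 38 women), the figure is 38 × 14/365 × 0.01 = 0.015. This bears on priority. It assumes consistent and correct contraceptive use, however, and leaves out conceptions shortly before Screening, which are among those a Day 1 test is best placed to catch.

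Three further points are fair:

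- A Day 1 urine test also misses very recent conception, so it reduces first-dose exposure and does not eliminate it.
- A Day 1 test alone leaves 83 days (85 with the window) without a scheduled test. It resolves the pre-dose gap and only shortens the on-treatment one.
- The documents give no embryofetal data, so the consequence of a short early exposure cannot be judged from them.

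These points limit the size of the issue. They do not supply a test on Day 1.

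**Conclusion.** The concern holds. Women of childbearing potential can be randomized and dosed in full compliance with the protocol on a pregnancy test 1 to 14 days old. Completers may then go up to 97 days (99 with the window) from Screening to Visit 4 without another scheduled test. This is a gap in the schedule rather than a contradiction between sections.

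The day counts rest only on the visit schedule and the absence of a Day 0. The number of women affected is not established: neither the share of women of childbearing potential nor embryofetal risk is given, and the small expected counts above cover only conceptions under compliant contraception. There is no effect on sample size, power, alpha or the primary analysis. It is a change that should be made because it is cheap and protects participants at the last point before exposure.

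**What to change.** - **Section 8.7.2:** schedule the urine pregnancy test for women of childbearing potential at Screening, at Visit 2 (Day 1) before randomization, and at Early Termination if indicated. State that a negative Visit 2 result is required before randomization and first dose.
- **Section 4.1, criterion 2:** add Visit 2 to the sentence on testing.
- **Appendix A:** mark Visit 2 in the urine pregnancy test row, and align SAP Table 1, which repeats the schedule.
- **Optional, for the clinical team:** repeat the test at Visit 3, before the two further kits are dispensed, and at Visit 4. The Visit 3 test would bring the longest interval down to 56 days (60 with windows).

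The cost is one urine test per woman of childbearing potential at a visit that already includes vital signs and blood sampling. The wording changes are short but form a protocol amendment, which needs IRB approval under Section 12.1. A positive result would stop a randomization, which is the purpose of the test.

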## Safety Follow-Up Period

Participants will return to the site for a Safety Follow-up Visit (Visit 5) approximately 4 weeks after the end of the Treatment Period for safety and PK assessments.

## DOSAGE FORMS AND ROUTE OF ADMINISTRATION:

The study drugs include obicetrapib 10 mg, ezetimibe 10 mg, and matching placebo for each. Participants will be randomized to receive combination therapy (obicetrapib 10 mg + ezetimibe 10 mg [administered as one 10 mg obicetrapib tablet and one 10 mg ezetimibe capsule]); obicetrapib monotherapy (obicetrapib 10 mg [administered as one 10 mg obicetrapib tablet and 1 placebo capsule]), or placebo (administered as 1 placebo tablet and 1 placebo capsule) on Day 1 to Day 84. Study drugs (1 tablet and 1 capsule) will be administered by the participant orally with water, once daily on Day 1 to Day 84 at approximately the same time each morning.

#### **EFFICACY VARIABLES:**

The primary efficacy endpoint is the percent change from Day 1 to Day 84 in LDL-C for the obicetrapib 10 mg + ezetimibe 10 mg combination treatment group compared with the placebo group.

The secondary efficacy endpoints include the following, in hierarchical order:

- Percent change from Day 1 to Day 84 in LDL-C for the obicetrapib 10 mg monotherapy treatment group compared with the placebo group;
- Percent change from Day 1 to Day 84 in ApoB for the obicetrapib 10 mg + ezetimibe 10 mg combination treatment group compared with the placebo group; and
- Percent change from Day 1 to Day 84 in ApoB for the obicetrapib 10 mg monotherapy treatment group compared with the placebo group.

The exploratory efficacy endpoints include the following:

- Percent change from Day 1 to Day 84 in non-HDL-C, VLDL-C, HDL-C, TG, ApoE, Lp(a), and HDL-ApoE for the obicetrapib 10 mg + ezetimibe 10 mg combination treatment group compared with the placebo group and for the obicetrapib 10 mg monotherapy treatment group compared with the placebo group; and
- Proportion of participants at Day 84 that achieve LDL-C <2.6 mmol/L (<100 mg/dL), LDL-C <1.8 mmol/L (<70 mg/dL), and LDL-C <1.3 mmol/L (<50 mg/dL) for the obicetrapib 10 mg + ezetimibe 10 mg combination treatment group compared with the placebo group and for the obicetrapib 10 mg monotherapy treatment group compared with the placebo group.

## PHARMACOKINETIC VARIABLES:

Plasma obicetrapib concentrations, both in combination with ezetimibe and as monotherapy, will be assessed at the scheduled PK collection times.

## **SAFETY VARIABLES:**

The safety and tolerability profile of obicetrapib 10 mg, both in combination with ezetimibe 10 mg and as monotherapy, will be assessed by clinical laboratory assessments (chemistry and hematology), vital signs, physical examinations, and the incidence of AEs.

## **STATISTICAL ANALYSES:**

A Statistical Analysis Plan (SAP) will be finalized before database lock. Any changes to the methods described in the SAP will be described and justified as needed in the Clinical Study Report. All study-collected data will be summarized by treatment group using descriptive statistics, graphs, and/or raw data listings. Descriptive statistics for continuous variables will include number of participants (n), mean, standard deviation (SD), median, minimum, and maximum values. Analysis of categorical variables will include frequency and percentage.

